#### Extension phase of the study:

Participants will be provided an option to continue the study for another 6 months. This is to ensure that all participants have access to the intervention (AHCL therapy), to collect safety data for 12 months, to ensure that the glycaemic improvement, if any, is sustained and to explore the behavioural patterns that could potentially affect control in the extension phase after novelty of the new intervention weans off.

- 1) *Group A:* The intervention group will continue to use AHCL therapy. Participants will be issued with enough consumables for the remainder of the study
- 2) **Group B:** The control group will be offered AHCL therapy (VISIT 9: commencement of AHCL: same as Visit 4)
- 3) Both groups will have additional visits at Visit 10 (9 months after randomisation) and Visit 11 (1 year after randomisation).
- 4) A random selection of participants at PCH, Perth will be offered semi-structured interview after V6

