#### VISIT 1: 1-2 hrs . (Eligibility Confirmation, Baseline data collection).

Information sheets will be provided in advance to participants who potentially fit inclusion criteria. Participants will be checked if they meet the inclusion criteria listed in Section 5.2. All post menarche females will have a urine  $\beta$ HCG test to exclude pregnancy. The following data will be recorded:

- 1. Consent signed by participant and investigator
- 2. Auxological
  - a. Height
  - b. Weight
  - c. BMI
  - d. Blood pressure
- 3. Demographic
  - a. Date of Birth
  - b. Gender
- 4. Diabetes clinical
  - a. Date of diagnosis
  - b. C-peptide (<0.1nmol/L cut off within 3 month of screening visit)
  - c. HbA1c
  - d. βHCG for all post menarche females
  - e. History of severe hypoglycaemia coma or convulsion or episodes requiring third party assistance (events in last 12 months).
  - f. History of diabetic ketoacidosis in the last 12 months
  - g. Hospital admissions in the last 12 months (DKA, Hyperglycaemia, Hypoglycaemia, Non diabetes related)
  - h. Total daily dose of insulin (mean of previous 7 days)
  - i. Co-morbidities and medications
  - j. Smoking and alcohol intake
  - k. Sensor data in the 2 weeks prior to the study (in participants on CGM).
- 5. Psychology measures:

Psychological scales will be administered on an electronic platform.

- a. Functional health status: Quality of Life: EQ-5D-3L for 12 to ≤25yrs
- b. Diabetes specific quality of life: PedsQL Child version (<13 yrs), Adolescent version (13 to <18yrs) and young adult version (18 to ≤25 yrs)

- c. Fear of hypoglycaemia: Hypoglycaemic Fear Survey-II Worry scale: 17 to ≤25yrs. Children's Hypoglycaemia Fear survey 12 to <17 yrs.
- d. Impact and Satisfaction: Diabetes Technology Questionnaire, Baseline version (all ages)
- e. Diabetes distress: Problem Areas in Diabetes (Paediatric version 12 to <18 yrs, Standard version ≥18 yrs, Parent version)
- f. Hypoglycaemia Awareness: Hypoglycaemia Awareness Scale (Gold Score) (all ages)
- g. Generalized Anxiety Disorder-7 and Patient Health Questionnaire-9 (12 to 25 years)
- h. Physical activity: The Active Australia Survey (all ages)

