- 4 Retinal photographs, performed as part of the routine annual screening, will be collected and retained for centralised assessment

5 Biomarkers

- 12mL of blood and 50mL of urine will be collected in a fasting state.
  - a. Cell Adhesion Molecules (CAM)S
  - b. Soluble vascular cell adhesion molecules sVCAM
  - c. Soluble intercellular adhesion molecules sICAM
  - d. s-e Selectin
  - e. Oxidized Low density lipoprotein
  - f. Myeloperoxidase.
  - g. MicroRNA signatures for arterial, renal and retinal complications
  - h. Telomerase
  - i. DNA methylation/acetylation
  - j. Glycomark
  - k. Isoprostanes and proteomics
  - I. Clotting profile

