#### Figure 2: Schematic representation of extension of study phase

VISIT 9 (Only for participants in the control arm transitioning to AHCL)

CSII to AHCL: Participant 780G 4.0, CGM education and AHCL training.

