#### Visit 9C: Commencement of AHCL (1 hour)

Once CGM data has been established for a minimum of 3 to 7 days, participant returns for face-toface instruction on AHCL use and initiation of Automode. During this visit, the sensor will be replaced, to demonstrate sensor warm up and AHCL initiation, and provide an opportunity for those unfamiliar with CGM use to practice a sensor change with supervision. Upon AHCL initiation, participants will be instructed to avoid excessive exercise for 48hrs while the algorithm adapts. Participants will subsequently have weekly communication via phone call or email for support for the following 4 weeks, and upload their pump weekly. Investigators will log all time spent training and communication with participant. Communication can be more often – as per clinical need, and logged.

Visit 9D: Review of AHCL (after 4 weeks from commencement of AHCL, 1 hour) Face-to-face meeting to upload insulin pump, review CareLink reports and revise pump settings (as necessary)

Participants will be issued with enough consumables for the study

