4.8 Expected duration of the trial and participant participation, including a description of the sequence and duration of all techniques or assessments to be performed, including follow-up (e.g. interventions, procedures, measurements, observations, laboratory investigations). Provide a schedule of assessments in a table if possible.

The trial is expected to take 2.6 years for recruitment and completion of study visits. For each participant, the expected study duration is 13 months. The schedule of assessments is provided in the table below.

						Visits	5					
	Screen	1	2	3	4*	5	6	7	8	9*	10	11
					Primary ph	ase				Exten	sion phase: O	Optional
Length of time of visit (hours)		1- 2	0.5	4 - 6	6	1	0.5	0.5	2	6	1	2
Weeks from Randomisation (+/- 3 weeks window)		-2	-1	0	1 to 4	12	23	24	26	28	36	52
Informed Consent		X										
C-peptide	х											
HbA1c	х	х		х		х			х		х	х
Auxological data		х				х			х		х	х
Diabetes clinical data		х		x		х			x		х	x
bHCG		х										
Insulin pump upload		х		х		х			х		х	х
Carbohydrate Counting				x								
Diabetes education				х								
Blinded sensor		х	х		х		х	х				
Pump training					х					х		
CGM training					х					х		
AHCL commencement					х					х		
Pump/CGM data clinical review				x	x	х			х	x	х	
Psychology measures		х		х		х			x	х	х	x
Retinal Scan				х					х			х
Biomarkers				х					х			
Face-to-face Interview#									х			х
Phone Interview (optional)								х				
Medtronic Questionnaire (optional)				x				x				
		* AHCL: Visit # Random se	4 has 4 visits ( ection of part	4A,4B, 40	Cand 4D); Vis Perth will be	it 9 has 4 visit offered sem	ts( 9A,9B, 9C a i-structured in	and 9D); Cont nterview at st	rol: V4 at 10 udv end (V8	weeks after r or V11)	andomisatior	1

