# 4.9 Criteria for the termination of the trial. Description of the discontinuation criteria for individual participants, parts of the trial and entire trial.

Study participation is voluntary, and participants may withdraw at any time. The DSMB will report to the ethics committees and investigators if stopping the trial is required.

In general, once a participant is randomised, he/she will remain in the study unless the investigator believes it is not safe for the participant to continue. However, the criteria below will be used to determine whether use of the AHCL should be discontinued for a participant.

- 1. Severe hypoglycaemia (seizure or coma or any episodes requiring third party assistance).
- 2. Severe diabetic ketoacidosis (venous ph <7.2)
- 3. Participant pregnancy
- 4. Non-compliance with the protocol or development of a new medical condition or need for chronic use of a medication which in the judgment of the investigator increases risk for the participant

If AHCL use is stopped according to the above criteria, but the participant is willing, they will remain in the trial and will continue to make all of the scheduled visits and participate in all monitoring. The primary analysis will be intention to treat. Since participants in the usual care arm are following their normal diabetes care regimen, there will be no change in their participation in the trial if they experience one of the events that would trigger stopping.

Criteria for Suspending/Stopping Overall Study

The DSMB will have the responsibility of determining if the overall study should be stopped. In case of a recurring system malfunction or participant safety issue observed with multiple participants, the overall study will be suspended while the problem is diagnosed. The study may resume if the underlying problem can be corrected by a protocol or system modification that will not invalidate the results obtained prior to suspension.

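### Controls who enter the extension first start AHCL about 30 weeks after the only scheduled pregnancy test, and no repeat test is listed

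*Protocol*

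**What the plan says.** **Testing.** In Protocol section 4.2, Visit 1 includes a urine "HCG test to exclude pregnancy", and the diabetes clinical data for that visit list "βHCG for all post menarche females". In the section 4.8 schedule the bHCG row has a single mark, under Visit 1.

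**First device start in controls.** For the control group the extension text reads: "The control group will be offered AHCL therapy (VISIT 9: commencement of AHCL: same as Visit 4". Visit 9 is "Only for participants in the control arm transitioning to AHCL". Auto Mode begins at Visit 9C, when the "participant returns for face-toface instruction on AHCL use and initiation of Automode". The AHCL commencement row of the schedule is marked at Visits 4 and 9.

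**Timing.** The schedule header is "Weeks from Randomisation (+/- 3 weeks window". It gives week -2 for Visit 1, weeks 1 to 4 for Visit 4, week 26 for Visit 8 and week 28 for Visit 9.

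**Pregnancy rules.** Section 5.3 excludes anyone who is pregnant or plans a pregnancy during the study. Section 4.9 lists "Participant pregnancy" among the criteria for deciding whether a participant should come off AHCL.

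**The concern.** The protocol tests for pregnancy shortly before participants in the AHCL arm first use the device. Controls reach the same step roughly half a year later with no new test. The likely cause is that Visit 9 repeats the Visit 4 steps. Visit 4 needed no test of its own because Visit 1 had only just taken place, so the steps carried over but the recent check did not.

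At stake is whether the protocol's own pregnancy rules can be applied when a control first starts the device. A test about 30 weeks old says almost nothing about pregnancy on that day. A control with an unrecognised pregnancy could be started on AHCL without the investigator having the information that sections 5.3 and 4.9 treat as relevant.

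**Working it through.** The protocol states no figure for this gap, so there is none to reproduce. All visit weeks below come from the section 4.8 schedule.

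1. **Is a later test listed anywhere?** The texts for Visits 3, 4A to 4D, 5, 8, 9A to 9D, 10 and 11 were read against the bHCG row. None lists a pregnancy test, which agrees with the single mark at Visit 1.

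2. **Age of the test when controls start, as planned.** Visit 9 minus Visit 1: 28 - (-2) = 30 weeks. Auto Mode itself starts at Visit 9C, after at least 3 to 7 days of sensor data (sensor-naive participants have 7 to 10 days of familiarisation), so the true figure is slightly above 30.

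3. **With the 3-week window.**
   - Window on both visits: shortest (28 - 3) - (-2 + 3) = 25 - 1 = 24 weeks; longest (28 + 3) - (-2 - 3) = 31 + 5 = 36 weeks.
   - Window on Visit 9 only: 25 + 2 = 27 to 31 + 2 = 33 weeks.

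4. **Same quantity in the AHCL arm.** As planned: 1 - (-2) = 3 to 4 - (-2) = 6 weeks. With both windows stretched as far as they go, (4 + 3) - (-2 - 3) = 12 weeks, which is still half the shortest gap for controls.

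5. **Where a repeat test should sit.** Visit 8 looks convenient, because the visit text has "12mL of blood and 50mL of urine will be collected in a fasting state". As planned, a Visit 8 result would be 28 - 26 = 2 weeks old at Visit 9, but with both windows it could be (28 + 3) - (26 - 3) = 31 - 23 = 8 weeks old. Appendix 16.11 also assigns the urine to biobanking and places the biomarker samples at V3 and V6. A test at Visit 9A, or otherwise before 9C, avoids both problems.

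6. **How many people.** 50 / 2 = 25 controls. If the 15% dropout in section 9.2 applies, 25 × 0.85 = 21.25. Only post-menarche females among them are concerned. The protocol gives no sex split. If 40 to 60% are post-menarche females (an assumption) and all remaining controls enter the extension, that is 21.25 × 0.4 = 8.5 to 25 × 0.6 = 15 tests. No pregnancy rate is given, so no expected number of pregnancies is claimed.

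**The case against.** **Entry-only testing is a coherent choice.** Pregnancy is excluded at entry by a test, and section 4.9 deals with pregnancy that arises later. Nothing promises repeat testing. This is fair: the two rules do not contradict each other. It does not answer the point, because the second rule depends on the pregnancy being known, and controls have their first start long after the only scheduled check.

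**Continuing AHCL users are not retested either.** This is true. By Visit 11 their only scheduled test is 52 - (-2) = 54 weeks old. A reader might infer that periodic testing is needed throughout. The documents do not support going that far: the one scheduled check comes before the first device start, and it is at that step that the arms differ.

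**Sites can test when they see reason to.** Nothing bars this, and Visit 8 includes a clinical review. But at Visit 1 the protocol did not leave testing to discretion, and an unrecognised pregnancy gives no prompt.

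**Other material may cover it.** Figure 2 and the consent pages are not available here, and the user guides are held separately. They may contain pregnancy instructions. The schedule would still show a single test.

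**Two further inferences to avoid.**
- A reader might take section 4.9 to forbid AHCL outright in pregnancy. Its wording is softer: the criteria serve to decide whether use should stop.
- A reader might also take the section 4.9 statement that usual-care participants carry on unchanged after a stopping event as letting a control known to be pregnant proceed to AHCL. The reason given there is that they are on their normal regimen, which ceases to apply once AHCL starts. A known pregnancy is covered.

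**Conclusion.** The point holds and is minor. As scheduled, controls first start AHCL about 30 weeks after the only pregnancy test (24 to 36 weeks with the window on both visits), against 3 to 6 weeks in the AHCL arm. The gap is in scheduled detection of an unrecognised pregnancy at first start; the pregnancy rules themselves are sound.

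It might be read as showing harm to participants or a threat to the trial result. Neither follows. The risk section names no pregnancy-specific hazard of the device, controls already use insulin pumps, and the extension is optional and begins after the 6-month comparison is complete. The conclusion rests on the schedule table as read and on the protocol's own exclusion and discontinuation criteria.

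**What to change.** In section 4.2, add a urine βHCG for post-menarche female controls at Visit 9A, or otherwise before Visit 9C, and state that AHCL is not started if the result is positive. Add the matching mark under Visit 9 in the bHCG row of the section 4.8 schedule.

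The cost is one urine test, of a kind the trial already uses, for each post-menarche female control entering the extension, at a visit that already takes place. No change to the analysis or the sample size is needed.

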#### Figure 2: Schematic representation of extension of study phase

VISIT 9 (Only for participants in the control arm transitioning to AHCL)

CSII to AHCL: Participant 780G 4.0, CGM education and AHCL training.

#### Visit 9A: Pump training and questionnaires (2 hours)

Participants will be trained on how to use the Medtronic 780G insulin pump. Participants will be provided with Roche Accu-Chek®glucometer along with the glucose strips for the study.

Questionnaires: INSPIRE (baseline), Diabetes Technology Questionnaire (baseline)

#### Visit 9B: CGM training (2 hours)

They will be instructed on how to link CGM on the Medtronic 780G pump and issued with Guardian Sensor 3 and the Guardian Link 3 transmitter, as well as CGM user guide. Initial low and high alarms will be set at 4.0mmol/L and 15mmol/L respectively, although these can be changed according to individual preference. Sensor naïve individuals will have familiarisation phase of 7 to 10 days to get used to wearing a sensor. Visit 9A and 9B could be combined for participants familiar with sensors.

#### Visit 9C: Commencement of AHCL (1 hour)

Once CGM data has been established for a minimum of 3 to 7 days, participant returns for face-toface instruction on AHCL use and initiation of Automode. During this visit, the sensor will be replaced, to demonstrate sensor warm up and AHCL initiation, and provide an opportunity for those unfamiliar with CGM use to practice a sensor change with supervision. Upon AHCL initiation, participants will be instructed to avoid excessive exercise for 48hrs while the algorithm adapts. Participants will subsequently have weekly communication via phone call or email for support for the following 4 weeks, and upload their pump weekly. Investigators will log all time spent training and communication with participant. Communication can be more often – as per clinical need, and logged.

Visit 9D: Review of AHCL (after 4 weeks from commencement of AHCL, 1 hour) Face-to-face meeting to upload insulin pump, review CareLink reports and revise pump settings (as necessary)

Participants will be issued with enough consumables for the study

#### VISIT 10 (9 months after randomisation; 1 hour)

The following data will be collected.

1. Auxological

#### Height, Weight, BMI, Blood pressure

- 2. Diabetes clinical
  - a. HbA1c
  - b. Total daily dose of insulin (mean of previous 7 days)
  - c. Carbohydrate ratios and insulin sensitivity factors
  - d. Pump upload (for both groups)
  - e. Sensor data in the 2 weeks prior to the study visit (in participants on CGM)
  - f. Clinical review
- 3. Psychological assessments
  - a. Functional health status: Quality of Life: EQ-5D-3L for 12 to ≤25yrs
  - b. Diabetes specific quality of life: PedsQL Child version (<13 yrs), Adolescent version (13 to <18 yrs) and young adult version (18 to ≤25 yrs)
  - c. Fear of hypoglycaemia: Hypoglycaemic Fear Survey-II Worry scale: 17 to ≤25yrs. Children's Hypoglycaemia Fear survey 12 to <17 yrs
  - d. Impact and Satisfaction: Diabetes Technology Questionnaire, follow-up version (all ages)
  - e. Diabetes distress: Problem Areas in Diabetes (Paediatric version 12 to <18 yrs, Standard version ≥18yrs, Parent version)
  - f. Hypoglycaemia Awareness: Hypoglycaemia Awareness Scale (Gold Score) (all ages)
  - g. Generalized Anxiety Disorder-7 and Patient Health Questionnaire-9 (12 to 25 years)
  - h. Physical activity: The Active Australia Survey (all ages)
  - i. INSPIRE questionnaire

Participants will be issued with enough consumables for the study

VISIT 11 (12 months after randomisation; 2 hours)

The following data will be collected at the end of the study.

- 1. Auxological
  - Height, Weight, BMI, Blood pressure
- 2. Diabetes clinical
  - 1. HbA1c
  - 2. Total daily dose of insulin (mean of previous 7 days)
  - 3. Carbohydrate ratios and insulin sensitivity factors
  - 4. Pump upload (for both groups)
  - 5. Sensor data in the 2 weeks prior to the study visit (in participants on CGM)
- 3. Psychological assessments
  - a. Functional health status: Quality of Life: EQ-5D-3L for 12 to ≤25yrs
  - b. Diabetes specific quality of life: PedsQL Child version (<13yrs), Adolescent version (13 to <18 yrs) and young adult version (18 to ≤25 yrs)
  - c. Fear of hypoglycaemia: Hypoglycaemic Fear Survey-II Worry scale: 17 to ≤25yrs. Children's Hypoglycaemia Fear survey 12 to <17 yrs.
  - d. Impact and Satisfaction: Diabetes Technology Questionnaire, follow-up version (all ages)Diabetes distress: Problem Areas in Diabetes (Paediatric version 12 to <18yrs, Standard version ≥18yrs, Parent version)
  - e. Hypoglycaemia Awareness: Hypoglycaemia Awareness Scale (Gold Score) (all ages)
  - f. Generalized Anxiety Disorder-7 and Patient Health Questionnaire-9 (12 to 25 years)
  - g. Physical activity: The Active Australia Survey (all ages)
  - h. INSPIRE questionnaire

4. Retinal photographs, performed as part of the routine annual screening, will be collected and retained for centralised assessment

5. Semi-structured interview: A random selection of participants at PCH, Perth will be offered semistructured interview within 4 weeks of completion of the study.

4.3 Measures taken to minimise/avoid bias, including randomisation and blinding.

Blinding is not possible, in this open label study. Minimisation will be used to allocate participants to study group based on the following balancing factors measured at baseline: age at Visit 1, HbA1c at Visit 1, and study site (MinimPy) (15). Participants will be allocated to the minimisation-preferred group with a probability to 70%. Minimisation is a method of ensuring excellent balance between

groups for known prognostic factors (16). Randomisation will be undertaken by the delegated persons at Perth Children's Hospital.

4.4 Maintenance of any blinding records or randomisation codes and procedures for breaking codes.

As this study is not blinded, the maintenance of breaking codes is not required.

4.5 Method of tracking implantable medical devices (if applicable).

Device serial numbers will be attributed to each study participant and recorded on an excel worksheet as they are issued. At the conclusion of the study, devices will be returned and checked off against the excel worksheet.

4.6 A description of the interventions or investigational product(s). For drug trials information regarding the dosage and dosage regimen, as well as a description of the dosage form, packaging, dispensing and labelling should be included.

The user manuals for 780G system are supplied electronically (they are large, and not appropriate for printing).

4.7 Accountability procedures for the investigational product(s) including the placebo(s) and comparator(s) (if applicable).

The study investigators will be responsible for patient safety during the study. The participants on AHCL will be contacted on a regular basis to monitor progress and help troubleshoot the problems.

4.8 Expected duration of the trial and participant participation, including a description of the sequence and duration of all techniques or assessments to be performed, including follow-up (e.g. interventions, procedures, measurements, observations, laboratory investigations). Provide a schedule of assessments in a table if possible.

The trial is expected to take 2.6 years for recruitment and completion of study visits. For each participant, the expected study duration is 13 months. The schedule of assessments is provided in the table below.

						Visits	5					
	Screen	1	2	3	4*	5	6	7	8	9*	10	11
					Primary ph	ase				Exten	sion phase: O	Optional
Length of time of visit (hours)		1- 2	0.5	4 - 6	6	1	0.5	0.5	2	6	1	2
Weeks from Randomisation (+/- 3 weeks window)		-2	-1	0	1 to 4	12	23	24	26	28	36	52
Informed Consent		X										
C-peptide	х											
HbA1c	х	х		х		х			х		х	х
Auxological data		х				х			х		х	х
Diabetes clinical data		х		x		х			x		х	x
bHCG		х										
Insulin pump upload		х		х		х			х		х	х
Carbohydrate Counting				x								
Diabetes education				х								
Blinded sensor		х	х		х		х	х				
Pump training					х					х		
CGM training					х					х		
AHCL commencement					х					х		
Pump/CGM data clinical review				x	x	х			х	x	х	
Psychology measures		х		х		х			x	х	х	x
Retinal Scan				х					х			х
Biomarkers				х					х			
Face-to-face Interview#									х			х
Phone Interview (optional)								х				
Medtronic Questionnaire (optional)				x				x				
		* AHCL: Visit # Random se	4 has 4 visits ( ection of part	4A,4B, 40	Cand 4D); Vis Perth will be	it 9 has 4 visit offered sem	ts( 9A,9B, 9C a i-structured in	and 9D); Cont nterview at st	rol: V4 at 10 udv end (V8	weeks after r or V11)	andomisatior	1

